1.0 Objectives

1.1 Purpose:

This is a pilot study to assess the following research aims:

- 1) **Is our approach is feasible?** Can we recruit smokers with SMI, deliver counseling and NRT, and keep participants engaged over the six months of intervention? Can we minimize attrition and loss to follow up?
- 2) **Are our proposed treatments acceptable?** How much counseling will we be able to deliver? How many participants will adhere to recommended NRT? Will participants utilize options for re-treatment after relapse or failing to initiate a quit/reduction attempt?
- 3) **How do 7-day abstinence outcomes** (and continuous abstinence, quit attempts, and reduced smoking) **compare between intervention and control conditions at 1- and 6-month follow-ups?**

2.0 Background

2.1 Significance of Research Question/Purpose:

There have been dramatic drops in overall smoking prevalence both in Minnesota and in the US as a whole (Cook et al. 2014; Steinberg et al. 2015). However, there are a number of subpopulations with a high continuing prevalence of tobacco use including those with serious mental illness (Gfroerer et al 2013). For those with severe mental illness (SMI) tobacco use is perhaps the leading factor implicated in their dramatically increased risk for morbidity and early mortality (Cook et al 2014; Kelly et al 2011; Lawn & Lucas, 2016; NIMH, Prochaska 2011). People with SMI die sooner than adults without SMI from illnesses such as heart disease, cancer, diabetes, and stroke (Kelly et al 2011; McGinty et al. 2012.) Clinical practitioners often fail to prioritize tobacco cessation because they are more focused on psychiatric issues (Lawn & Lucas, 2016; Prochaska 2011).

There is evidence that smokers with SMI want to quit, are receptive to offers of cessation treatment, and can quit successfully. We are seeking to deliver an intensive but low cost and widely disseminable intervention to smokers with SMI that addresses tobacco dependence as a chronic disease.

2.2 Preliminary Data:

This is a pilot study with the intent of gathering preliminary data on this subject.

2.3 Existing Literature:

The 2008 US Clinical Practice Guideline Treating Tobacco Use and Dependence (on which [name] was a panel member) states that all

smokers with psychiatric disorders should be offered tobacco dependence treatment (AHRQ 2018; Fiore et al 2008). The American Psychiatric Association recommends that psychiatrists assess the smoking status of all patients, including readiness to quit, level of nicotine dependence and previous quitting history. Clinicians are encouraged to use this information to provide explicit advice to motivate patients to stop smoking (Prochaska, Gill, & Hall 2004).

3.0 Study Endpoints/Events/Outcomes

3.1 Primary Endpoint/Event/Outcome:

The primary outcome of our study is to determine the proportion of patients in the intervention and control conditions who achieve 7-day point prevalence abstinence at 8 weeks and 6 months after enrollment

3.2 Secondary Endpoint(s)/Event(s)/Outcome(s):

The secondary outcome of our study is to determine the proportion of patients in the intervention and control condition who achieve continuous abstinence, reduced number of cigarettes per day, and self-reported minimum 24 hour quit attempts.

4.0 Study Intervention(s)/Investigational Agent(s)

4.1 Description:

This randomized trial will include in-person meetings and phone counseling sessions with participants. We will seek to deliver treatment that optimally follows current guidelines, provides for substantial counseling support, includes an option for NRT, and keeps patients engaged in quitting.

Drug/Device Handling:

We will be using different types of NRT in this study including lozenge and patches. Only study staff who have been trained to follow standard operating procedures for handling and distributing the NRT drugs used in this study will have access to them. These NRT drugs are currently FDA approved, on the market, over-the-counter medicines that do not require a doctor or pharmacist for distribution. All NRT drugs will be kept in the locked Drug Supply Room at the ECRC. The study coordinator will maintain a Drug Accountability Record of the purchase and distribution of all NRT drugs.

Patients will be offered the nicotine patch (dose based on number of cigarettes per day) and/or the nicotine lozenge (2 or 4 mg if less or greater than 30 minutes to first cigarette in the morning respectively) depending on participant preference and how much they are smoking based on FDA guidelines for use. We will follow FDA guidelines for the length of time a participant should use their NRT, anywhere between 8 and 12 weeks, depending on cigarette use, addiction level, and type of NRT. Participants will receive a four-week supply of NRT during the baseline visit. If participants are using and want to continue using NRT,

the remainder of their supply will be distributed to them at 4 weeks. We will either mail subsequent NRT in puncture resistant packaging to the participants or participants come to the ECRC to pick up their remaining supply.

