21.2 International Research: N/A

22.0 Multi-Site Research: N/A

23.0 Resources Available

23.1 Resources Available:

[name] has experience in recruiting participants from the HCMC clinics and we have the support of the Clinical Research Advocate at the UMN clinics to assist in recruitment of patients. We have access to the patients attending UMN and HCMC smoking cessation and psychiatric clinics as our base for recruiting potential participants. We plan to recruit 60 into the study.

Study staff will be housed in the Division of Epidemiology and Community Health and ECRC. Within the Division, we have access to all needed office supplies, printers, and technical assistance. The division also offers administrative support for research projects. The study coordinator will also have space designated to the study at the ECRC building. This is where the all in-person visits will take place. The ECRC also has basic office support and resources available for study use. In addition, ECRC has an Emergency Response Team (ALERT) that responds to any emergency that may occur within the clinic. All study staff members have experience in conducting human subjects research and will be trained by the PI and/or the study coordinator on standard operating procedures that need to be followed for every aspect of the study.

We will be following the UMN Psychiatry Department's "Unanticipated Problem/Crisis Communication Plan for Research Activity" flowchart for any psychiatric issues that arise while we are meeting or speaking with our study participants. We will also be employing a clinically licensed UMN employee (TBD) who will provide psychiatric safety information and guidance to study staff.

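### Read in order, the lozenge rule in section 4.1 gives 2 mg below 30 minutes to first cigarette and 4 mg above; on two assumptions the protocol does not state, this is inverted and should be checked against the labelling.

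*Combined protocol and SAP*

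**What the plan says.** Section 4.1, under Drug/Device Handling, offers the patch and/or the lozenge. The patch has its "dose based on number of cigarettes per day". The strength of the lozenge is set by a parenthesis: "nicotine lozenge (2 or 4 mg if less or greater than 30 minutes to first cigarette in the morning respectively". The same sentence makes the offer as a whole "depending on participant preference and how much they are smoking based on FDA guidelines for use". The next sentence sets length of use, between 8 and 12 weeks, "depending on cigarette use, addiction level, and type of NRT".

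On dispensing, section 4.1 limits access to staff "trained to follow standard operating procedures for handling and distributing the NRT drugs used in this study" and describes the products as "currently FDA approved, on the market, over-the-counter medicines that do not require a doctor or pharmacist for distribution". A four-week supply is given at baseline. For those who want to continue, "the remainder of their supply will be distributed to them at 4 weeks". Section 23.1 adds that staff will be "trained by the PI and/or the study coordinator on standard operating procedures that need to be followed for every aspect of the study". The SOP and the FDA text are not reproduced.

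**The concern.** The parenthesis is the only instruction in the documents that tells staff which lozenge strength to hand out. Its word order sends the weaker lozenge to people who smoke soonest after waking. If those are the more dependent smokers, and if more dependent smokers should get the stronger product, the rule does the opposite of what the rest of the section sets out to do. A transposed phrase would be a natural explanation, since the protocol gives no rationale for a reversed regimen.

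The lozenge is not a marginal product here. Section 5.2 offers it to those who want to quit and also names it as a substitute for individual cigarettes in those who choose to cut down. A wrong strength could affect tolerability and adherence to recommended NRT, which is part of aim 2 in section 1.1, and the exploratory smoking outcomes of aim 3. Section 15.1 intends those outcomes to inform effect sizes for a possible larger trial, so an uncorrected sentence could also be carried forward.

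**Working it through.** The plan gives no figure to reproduce, so the check is a reading of the text with one small ratio.

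**1. Literal pairing (section 4.1).** The strengths are listed as 2, then 4. The conditions are listed as less, then greater. The word *respectively* fixes the order.

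| Time to first cigarette | Strength as written |
|---|---|
| Less than 30 minutes | 2 mg |
| Exactly 30 minutes | none assigned |
| More than 30 minutes | 4 mg |

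The gap at exactly 30 minutes is only a missing detail.

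**2. Is there another rule?** Section 5.2 (Session 1, the follow-up calls, the control group), section 11.4 (Payment) and section 17.1 (monitoring) give no lozenge strength. Time to first cigarette is mentioned only in section 4.1. Nothing in the documents corrects or contradicts the pairing.

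**3. Direction.** Two premises are needed, and neither is in the documents.

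- Assumption A: an earlier first cigarette marks greater nicotine dependence.
- Assumption B: greater dependence calls for the higher strength.

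With A and B, less than 30 minutes means more dependent, which means 4 mg. The text says 2 mg. More than 30 minutes means less dependent, which means 2 mg. The text says 4 mg. Both halves are reversed. Without both premises, the documents show no error.

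**4. What the neighbouring text supports.** Patch dose follows cigarettes per day, the offer follows smoking level under FDA guidelines, and length of use follows cigarette use and addiction level. This fits B as the general logic of the section. It does not prove B, because no direction or cut-point is given for the patch and addiction level is named only for length of use. Nothing in the section bears on A.

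**5. Size per lozenge, if inverted and followed literally.**

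- Below 30 minutes: strength given / strength intended = 2/4 = 0.5.
- Above 30 minutes: 4/2 = 2.

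This would apply to every lozenge user not at exactly 30 minutes, however participants split around that point. It describes one lozenge. It is not daily nicotine intake, because lozenges per day are not given and a patch may be used as well.

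**6. How many participants.** The minimum is zero, if staff follow the labelling or a correct SOP. No secure maximum can be given. Lozenge uptake is not stated. Section 5.2 lists NRT only among the intervention activities, while sections 4.1 and 11.4 describe its supply without naming an arm.

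**7. Effect on the statistics.** Section 15.2 says the study is not powered for abstinence. The model in section 15.3 does not specify NRT strength as a term. Neither the sample size nor the analysis depends on the phrase.

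**The case against.** The strongest reply is that the documents do not establish an error. The direction rests on A and B, and the standard that would settle it, the FDA text, is not reproduced. The support within section 4.1 is indirect. This stands, and it is why the point is conditional and asks for a check before any correction.

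The second reply is that safeguards may make the wording harmless. The sentence itself defers to FDA guidelines. The products are approved over-the-counter medicines handled only by SOP-trained staff. Under section 5.2, Session 1 follows clinical practice guidelines and the counselor goes over correct use; later calls ask about NRT use and side effects and consider alternatives. Section 17.1 allows individual adjustments after adverse reactions. This stands in part, since any of these could prevent literal misdosing. None is described as a check on lozenge strength, however. The medicines need no doctor or pharmacist, no strength review is mentioned when the remaining supply goes out at 4 weeks, and the calls come after Session 1. If the SOP copies the parenthesis, nothing described would clearly catch it. If the labelling runs the other way, staff who follow it depart from the protocol's literal words, so the sentence needs settling in either case.

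A reader might infer that participants were, or will be, given the wrong strength. The documents do not support that: they do not show which strength was dispensed, what the SOP says, or how many chose the lozenge.

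**Conclusion.** The point holds in conditional form. That the literal rule gives 2 mg below 30 minutes and 4 mg above is certain, as is the absence of any other strength rule. That the rule is inverted depends on assumptions A and B and has to be confirmed from the labelling. A transposition is a reasonable suspicion, but the documents alone cannot prove one.

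If the inversion is confirmed and the words are followed, each affected lozenge has half or double the intended strength, with under-dosing in the more dependent users and over-dosing in the less dependent. The number of people affected is unknown and may be zero. The consequence is for treatment delivery, safety and NRT adherence, not for sample size or analysis. It should be fixed, because this is the only stated strength rule for a study medicine and the correction is very small. Confidence is medium.

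**What to change.** 1. Check the pairing against the product labelling.
2. If the inversion is confirmed, restate the rule in section 4.1 as one sentence per strength, without *respectively*: 4 mg for the shorter time to first cigarette, 2 mg for the longer. Place exactly 30 minutes on the side the labelling gives.
3. Confirm that the dispensing SOP carries the same pairing.
4. Only if the SOP is also inverted, compare strengths already dispensed with time to first cigarette, using the Drug Accountability Record and the baseline data. Section 5.2 says only that nicotine dependence is collected at baseline, so this is possible only where that item was recorded.

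The cost is a labelling check, a one-sentence protocol correction and an SOP check. No extra participants, visits or procedures are needed.

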4.2 Biosafety: N/A

4.3 Stem Cells: N/A

5.0 Procedures Involved

5.1 Study Design:

This is a randomized clinical trial that will enroll patients with documented SMI (ICD-10 codes) including schizophrenia, any other psychotic disorder, bipolar I and II disorder, and/or recurrent/chronic major depressive disorder into either a counseling intensive smoking cessation program or the control group.

5.2 Study Procedures:

This intervention is tailored to the needs of SMI smokers including addressing barriers to quitting and the need for continued supportive contact. Following is an outline of the study procedures:

Baseline assessment

Trained study staff will:

- Conduct informed consent
- Collect demographic and smoking history information along with current interest in quitting, readiness to quit, confidence in ability to quit, and nicotine dependence. We also will include mood, general psychiatric health, and quality of life questionnaires. (SMI Smokers BL Interview V1.1, SMI Smokers BL Self Report V1.1)
- Collect the name and phone number of an additional contact. Study staff will call the contact in the case of an emergency with the participant or if staff are unable to reach the participant for study visits. Staff will explain the two reasons for needing the additional contact person to the participant during the baseline visit.
- Randomize participants: prior to the baseline visit, we will complete a 1 to 1 non-stratified randomization. The randomization results will be put in envelopes to be opened during the baseline visit, determining if a participant will be allocated to the intervention or the control group.
- Conduct or schedule session one with those in the intervention group
- Distribute materials/resources to all participants.

Follow up assessments:

- Conducted at 8 weeks and 6 months post baseline assessment. (SMI Smokers 8 Week Interview V1.0, SMI Smokers 6 Month Interview V1.0,

and SMI Smokers 8W 6M Self Report V1.0, Study Satisfaction Survey V1.0 will be administered only at the 6 month assessment and only to participants in the Intervention group).

- Conducted in person when possible, but a phone option will be available.
- Measures will include current smoking status, quit attempts, self-reported number of cigarettes per day for those who currently are smoking, and interest and confidence in quitting/continued abstinence.
- Reported 7-day abstinence at 8 weeks and 6 months will be validated by an expired carbon monoxide sample.

The intervention group activities include the following:

Session 1:

- 1 hour in person visit
- Will include population specific information about smoking and mental illness
- Counselor will provide a strong and personalized recommendation to quit
- The remainder of Session 1 will be guided by current clinical practice guidelines and the National Cancer Institute's Clearing the Air patient workbook
 - The counselor will cover: past attempts to quit (reframing these as learning opportunities), and education on the risks of smoking and benefits of quitting both in general and for SMI patients.
 - Emphasis will be placed upon personal reasons for quitting or reducing number of cigarettes, especially those that are intrinsic
 - The counselor will discuss coping strategies and will focus on identifying strategies that are appropriate for the individual patient.
 - The counselor will provide tips for how to elicit support and for managing cravings
 - The counselor will address planning for behavior change including preparation for a quit date when applicable and anticipating challenging situations
- For those patients who initially choose to reduce rather than quit, the focus will be on reduction strategies including substituting NRT lozenge for individual cigarettes
- Patients who want to quit will be offered a nicotine patch and/or the nicotine lozenge.
- The counselor will review correct placement and/or use.
- Counselor also will address the efficacy and safety of nicotine replacement

Follow up counseling calls:

- Counselors will make 6 calls over 8 weeks after initial in person session.
- There will be assessments of current smoking status, NRT use and side

effects, and motivation to continue/restart quitting/reduction plan. NRT use will be encouraged.

- For those who have discontinued use or who have encountered problems with NRT, the counselor will review the patient's experience and consider alternatives including advice to try a different form of NRT
- If the patient is abstinent, the counselor will reinforce their success, discuss any times since the previous session when the participant struggled with cravings, will review strategies for managing triggers and cravings, and problem solve upcoming challenges to continued abstinence.
- If the patient is smoking, the counselor will reinforce any efforts that the patient made including cutting down or attempting to quit and will apply brief motivational strategies to prompt further reduction or a subsequent quit attempt.
- The counselor will seek to keep all patients engaged in active behavior change.

Additional counseling phone calls:

- 3 calls (minimum) from 8 weeks to 6 months
- Telephone calls will be supplemented by supportive text messages when agreed to by participants during this phase.
- Those who choose to initiate a new quit/reduction attempt will be eligible for multiple telephone calls (up to six in one or more new rounds of intervention before the end of 6 months).

The control group activities include the following:

Participants in the control group will complete the baseline assessment interview and self-report and follow-up assessments at 8 weeks and 6 months. They will also receive information about smoking and mental illness and referrals to the QUITPLAN helpline.

Contact Letters

Participants in both the intervention and control groups will receive three letters by mail from the study. The first letter will be mailed approximately four weeks post baseline, the second approximately six weeks post 8-week assessment, and the last letter will be mailed approximately 12 weeks post 8-week assessment (Contact Letters V1.0)

5.3 Study Duration:

This study will enroll participants beginning fall of 2018 and continue enrollment until we recruit 60 participants or until time will no longer allow us to recruit based on the funding deadlines. As this is a two-year grant with no opportunity for a no-cost extension, all study related activities should be completed within two years.

5.4 Individually Identifiable Health Information:

As part of the recruitment process, study staff at UMN will call potential participants whose names are on a list they receive from the Clinical Research Advocate within the UMN Department of Psychiatry. The people on this list have given written consent and have agreed to be contacted for study recruitment purposes. UMN staff may also receive calls from patients who self-identify in response to flyers hung in the UMN Department of Psychiatry. If an individual self-identifies and diagnosis needs to be verified, [name], an Assistant professor in the Department of Psychiatry, clinical psychologist, and Co I on this study, is authorized to review patient charts and can verify diagnosis for study purposes. Patients who are taking the medications Clozapine/Clozaril or Chantix/Varenicline will not be allowed in the study. [name] will also be reviewing charts to ensure otherwise eligible patients are not currently taking these medications. HCMC screeners will be accessing individual medical charts of HCMC patients to verify a diagnosis of SMI, collect contact information, and perform screening.

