Patients will receive a \$30 incentive for completing the baseline survey, a \$50 incentive for completing the 8-week survey, and a \$50 incentive for completing the final survey at six months post baseline assessment. All counseling sessions and related materials, including NRT, will be given to the patients free of charge. Participants will also be given \$30 to help cover the cost of transportation to the in-person sessions. If a candidate comes in

for the baseline visit and is deemed unable to give informed consent based on the results of the UCSD Brief Assessment of Capacity to Consent for Minimal Risk research, they will be given \$10 to help with travel expenses for the appointment.

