15.0 Statistical Considerations

15.1 Data Analysis Plan:

Feasibility analyses (e.g. recruitment rate, retention rate) and acceptability analyses (e.g., satisfaction scores, sessions attended, uptake of NRT) will be primarily descriptive. Given the limited number of participants, primary and secondary outcome analyses will be exploratory and will be used for effect size estimates for a potential larger future trial.

15.2 Power Analysis:

Although we are not powered to detect differences in abstinence, the current study will provide a necessary demonstration of the feasibility of our approach.

15.3 Statistical Analysis:

All analyses will be conducted on the intent to treat sample, with all randomized participants included in the analysis. We will estimate the effect of the intervention on smoking cessation (biochemically verified 7-day point prevalence abstinence) over 6 months using a single repeated measures regression model implemented with generalized estimating equations (GEE) and robust standard errors. Specifically, we will regress smoking status on intervention group and potential covariates using binomial errors, a logit link function, and a working unstructured correlation to accommodate within-subject correlation. For continuous secondary outcomes we will use linear regression models.

15.4 Data Integrity:

All study staffed will be trained on how to collect and store data. Data quality will be evaluated by study staff through review and assessment of gathered data to ensure completeness. Data will be kept in locked files or on a secure server, to both of which only authorized study personnel will have access. All identifying data will be stored separately.

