20.6 Adults Unable to Consent: N/A

21.0 Setting

21.1 Research Sites:

Recruitment of potential participants will take place in HCMC and UMN clinics. Research procedures, including all in-person visits, will take place in the ECRC building.

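### Does allowing telephone follow-up undermine the CO-verified abstinence outcome?

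*Combined protocol and SAP*

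**What the plan says.** Section 5.2 describes the 8-week and 6-month assessments in a short list. One item gives the mode: "Conducted in person when possible, but a phone option will be available". Another gives the verification rule: "Reported 7-day abstinence at 8 weeks and 6 months will be validated by an expired carbon monoxide sample". That rule makes no exception for telephone assessments.

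Section 3.1 defines the primary outcome as the proportion in each arm "who achieve 7-day point prevalence abstinence at 8 weeks and 6 months after enrollment" and does not mention verification. Section 15.3 does: the model estimates the effect on "smoking cessation (biochemically verified 7-day point prevalence abstinence) over 6 months". It adds: "All analyses will be conducted on the intent to treat sample, with all randomized participants included in the analysis".

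On logistics, Section 21.1 says "Research procedures, including all in-person visits, will take place in the ECRC building". Section 11.4 pays a $50 "incentive for completing the 8-week survey" and the same at 6 months. It also gives $30 toward transport to in-person sessions. Neither payment is tied to a CO sample.

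On purpose, Section 15.1 says that "primary and secondary outcome analyses will be exploratory and will be used for effect size estimates for a potential larger future trial", and Section 15.2 states that the study is not powered for abstinence.

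**The concern.** The two items in Section 5.2 seem to pull against each other. A participant who reports smoking by telephone has given a usable outcome. A participant who reports abstinence by telephone has not, because the analysed outcome needs a breath sample. The loss therefore falls on one side only. If no sample is ever obtained, verified abstinence will sit below true abstinence in both arms.

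Two rules are not written down: how CO is obtained after a telephone report, and whether a report without CO counts as smoking, as missing or as abstinent. Because Section 3.1 leaves out verification, an analyst could in principle score the same participant in different ways. If telephone use also differed by arm, the treatment effect could move in either direction. The estimates are meant to inform a larger trial, so a distorted rate could be carried forward.

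**Working it through.** **Is there a contradiction?** No. Section 5.2 requires CO for every reported abstinence, and Section 21.1 names the place where it can be collected. A telephone reporter still owes a sample. What is unstated is the route and timing.

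**Does the plan imply a coding rule?** Largely. Section 15.3 names a verified outcome and keeps all randomized participants. A report that was never verified does not meet that definition, and dropping the participant conflicts with the analysis set. Not abstinent is the natural reading, although it is not spelled out.

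**How large could the effect be?** The documents give no abstinence rate and no telephone share, so there is no stated figure to reproduce. Every rate and share below is an assumption. Only the arm size of about 30 (Section 11.1) comes from the plan.

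Let p be the share truly abstinent and confirmable by CO, and f the share of those followed by telephone with no CO ever obtained.

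- Coded smoking: rate = p(1 − f).
- Only the unverified abstinence reports set to missing: rate = p(1 − f)/(1 − pf).
- All telephone assessments set to missing, with mode unrelated to abstinence: rate = p, so nothing is lost.
- Self-report accepted: no loss from missing CO, but the outcome is no longer verified.

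With p = 0.20 in one arm and 0.10 in the other, and equal f:

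| f | Rule | Rates | Difference | Odds ratio |
|---|---|---|---|---|
| 0 | – | 20% v 10% | 10 points | 2.25 |
| 0.2 | smoking | 16% v 8% | 8.0 | 2.19 |
| 0.4 | smoking | 12% v 6% | 6.0 | 2.14 |
| 0.2 | missing | 16.7% v 8.2% | 8.5 | 2.25 |
| 0.4 | missing | 13.0% v 6.25% | 6.8 | 2.25 |

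Example for f = 0.4, smoking: (0.12/0.88)/(0.06/0.94) = 2.14. Under the missing rule the odds in each arm are p(1 − f)/(1 − p), so the factor 1 − f cancels and the odds ratio stays at 2.25.

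In people, at p = 0.20 and 30 per arm, f = 0.2 or 0.4 means 30 × 0.20 × f = 1.2 or 2.4 participants.

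**Against sampling error.** The 95% half-width for 20% v 10% at 30 per arm is 1.96 × √(0.2×0.8/30 + 0.1×0.9/30) = 0.179, about 18 points. The loss of 2 to 4 points in the difference is small beside it.

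**Unequal telephone use (coded smoking, 20% v 10%).** With f = 0.3 in control and 0.1 in intervention, the rates are 7% and 18%, odds ratio 2.92. Reversed, they are 9% and 14%, odds ratio 1.65. The differences are 11 and 5 points, against a true 10. A milder split, 30% v 40% with both arms at p = 0.20, gives 14% v 12%, or 4.2 v 3.6 of 30, a shift of 0.6 of a participant.

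**What would a formal recall visit do?** With attendance a among telephone reporters, rate = p(1 − f + fa). At p = 0.20 and f = 0.4, the rate runs from 12% (a = 0) to 20% (a = 1). The visits needed are 60 × (p + u) × f per time point, where u is the share falsely reporting abstinence. With u = 0 and f = 0.2 this is 2.4; with u = 0.05 and f = 0.4 it is 6.0. Over two time points that is 4.8 to 12 visits. If attendance were 75% in one arm and 25% in the other, with equal p = 0.20 and f = 0.4, the rates would be 18% v 14%. That is 5.4 v 4.2 of 30, an imbalance of 1.2 participants where equal telephone use alone creates none.

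**The case for a change.** The strongest case for a change is that the repair looks cheap. A sentence on how CO is obtained, a coding rule, a self-report sensitivity analysis and a table of assessment mode and CO completion by arm cost little. They would also tell the planners of a larger trial how much of the shortfall is due to missing samples. Equal telephone use cannot be taken for granted either: the intervention arm has far more contact after baseline than the control arm, and the documents are silent on mode by arm.

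Much of this stands as fact. The route and the coding rule are not in the text, and unequal use could move the odds ratio either way.

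What does not stand is the step from silence to defect. Section 5.2 presents itself as an outline and cites separate 8-week and 6-month interview forms, and Section 23.1 refers to standard operating procedures for all parts of the study. These are not available here and may already cover the point. The coding rule would record what Section 15.3 already implies, and the table and sensitivity analysis are routine reporting that needs no amendment. The one element that would alter conduct is a fixed recall with the 7-day question repeated. It would hold telephone reporters to a stricter test than in-person participants, since they must be abstinent at both call and visit, and it depends on attendance by people who may have used the telephone because they could not attend.

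**Conclusion.** No change is needed. The plan omits logistics and a coding detail; it does not contradict itself. Followed as written, it still calls for CO after a telephone report, and staff and analysts would sensibly fill the rest: ask the reporter to come in, and count an unverified report as not abstinent.

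If no CO were obtained after any telephone report, the rate at an assumed 20% abstinence would fall by 4 to 8 points for telephone shares of 20% to 40% among abstainers. With equal use by arm the odds ratio would go from 2.25 to 2.14 at the lowest. These sizes rest wholly on assumed inputs, and in-person assessment is the stated default. Unequal use could move the estimate more, in either direction, but nothing in the documents shows that it will occur.

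The abstinence analyses are exploratory and unpowered. The lower rate is also the correct value of the verified outcome under this follow-up design. It is a fair planning figure for a larger trial that keeps the same telephone option, and would mislead only one that verifies every report. The telephone option supports retention, which the pilot sets out to measure, and a recall requirement is a debatable trade-off, not a clear gain.
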